4.2 Treatment Logistics and Accountability

4.2.1 Packaging, Labeling, and Storage

Intracanalicular dexamethasone insert must be stored in a secure area accessible only to the Investigator and their designee(s) and refrigerated and stored between 2° C and 8° C. Intracanalicular dexamethasone insert contains 0.4 mg dexamethasone and is designed to provide a sustained and tapered release of therapeutic levels of dexamethasone to the ocular surface for up to 30 days for the reduction of post-surgical inflammation and pain associated with ocular surgery. Dexamethasone is an anti-inflammatory 9-fluoro-glucocorticoid (also termed a glucocorticoid agonist) and is the active ingredient found in MAXIDEX® 0.1% (dexamethasone ophthalmic suspension), which contains approximately 50 µg of dexamethasone per drop.

Study inserts will be supplied by Ocular Therapeutix in a sealed foil pouch containing one intracanalicular dexamethasone insert in a foam carrier.

Study inserts will be shipped to the site via overnight shipping using cold packs to maintain a temperature of 2° to 8° C. The Investigator, or an approved representative (e.g. pharmacist), will ensure that all study drug inserts are stored in a secured area, under recommended storage conditions and in accordance with applicable regulatory requirements. The shipping box is to be opened and stored immediately at the site in a refrigerator intended

for investigational products at a temperature of 2° to 8°C.

When the insert is removed from the refrigerator, it should be visually inspected. Exposure of the insert to temperatures outside these limits it not recommended. Records of actual storage conditions (i.e. temperature log) at the study site must be maintained; and must include a record of the dates, when the refrigerator was checked, the initials of person checking, and the temperature.

4.2.2 Supply and Disposition of Treatments

Study insert will be shipped at a temperature of 2° to 8°C to the investigator as needed during the study.

4.2.3 Treatment Accountability

All study insert accountability records will be kept current.

The investigator will account for all opened and unopened packaging of study inserts. These records will contain the dates, quantity, and study medication

- Inserted in each patient,
- disposed of at the site or returned to Ocular Therapeutix

All accountability records will be made available for inspection by regulatory agency inspectors.

4.3 Concomitant Medications and Procedures

At the discretion of their physician, patients may continue to receive all medications and standard treatments administered for other conditions.

5. STUDY SCHEDULE OF EVENTS AND VISIT DESCRIPTIONS

5.1 Schedule of Events

Study assessments and procedures are presented by visit in Table 1.

 Table 1
 Schedule of Events

Study Procedure	Screening/ Baseline	Surgica l Visit Day 0	Day 1	Day 7	Day 30	3 MTH post-op	Early Termi nation
Visit	VISIT 1	VISIT 2	VISIT 3	VISIT 4	VISIT 5	VISIT 6	
Windows for Visits	(Day -90 to - 1)		(+/- 2 days)	(+/- 2 days)	(+/- 7 days)	(+/- 14 days)	
Inclusion/Exclusion	X						
Informed Consent	X						
Demographics	X						
Medical History and Concurrent Illnesses	X						
Concomitant Medications (inc. glaucoma meds and supp. prednisolone)	X		X	X	X	X	
BCVA (ETDRS at 4m)	X		X	X	X	X	
Visual field mean deviation	X					X	
Ophthalmic Examination (dilated fundus exam)	X		X	X	X	X	
Cataract density grade (scale 1 to 4) and type	X						
Glaucoma type and severity	X						
OCT RNFL & Macula	X					X	
Intraocular Pressure (Goldmann and CATS)	X		X	X	X	X	
Corneal Endothelial Specular Microscopy	X					X	
Gonioscopy	X					X	
Ocular Response Analyzer	X					X	
Pachymeter	X						
Indirect Ophthalmoscope	X					X	
Indicate the incision type, location, and size (mm)		X					
Type of IOL(e.g. monofocal, toric, multifocal, etc.) and lens power	X	X					
Type of MIGS device	X	X					
Record any surgical complications		X					X
Subject reported AEs prior to or after surgery	X		X	X	X	X	X
Intracanalicular dexamethasone insert		X					
Ocular Comfort Index					X	X	
Anterior chamber cell count			X	X	X	X	
Anterior chamber cell flare			X	X	X	X	
Insert Visualization			X	X	X	X	
Prescribe post-operative topical therapy regimen			X				

5.2 Study Visit Descriptions

5.2.1 Study Procedures

Screening/Baseline (Day -90 to-1)

After the patient has provided informed consent, the following information will be collected:

- 1. Inclusion/exclusion
- 2. Demographics
- 3. Medical history and concurrent illnesses
- 4. Concomitant medications
- 5. Best-corrected visual acuity as measured by ETDRS chart at 4m
- 6. Visual field mean deviation
- 7. Ophthalmic examination
- 8. Grade cataract density and identify type
- 9. Glaucoma type and severity
- 10. OCT RNFL & Macula
- 11. Goldmann Intraocular pressure and CATS intraocular pressure
- 12. Corneal endothelial specular microscopy
- 13. Gonioscopy
- 14. Ocular Response Analyzer
- 15. Pachymeter
- 16. Indirect ophthalmoscope
- 17. Type of IOL
- 18. Type of MIGS device (Hydrus, iStent, canaloplasty, or Kahook Dual-Blade)
- 19. Subject reported AEs prior to surgery

Surgical visit/Day 0

- 1. Indicate the incision type, location, and size
- 2. Type of IOL
- 3. Type of MIGS device (Hydrus, iStent, canaloplasty, or Kahook Dual-Blade)
- 4. Record any surgical complications
- 5. Intracanicular dexamethasone insert

Day 1 postop (+/- 2 days)

- 1. Concomitant medications
- 2. Best-corrected visual acuity as measured by ETDRS chart at 4m
- 3. Ophthalmic examination
- 4. Goldmann Intraocular pressure and CATS intraocular pressure
- 5. Subject reported AEs after surgery
- 6. Anterior chamber cell count
- 7. Anterior chamber cell flare
- 8. Insert Visualization
- 9. Prescribe post-operative topical therapy regimen

Day 7 postop (+/- 2 days)

1. Concomitant medications

October 18, 2020 Page 13

- 2. Best-corrected visual acuity as measured by ETDRS chart at 4m
- 3. Ophthalmic examination
- 4. Goldmann Intraocular pressure and CATS intraocular pressure
- 5. Subject reported AEs after surgery
- 6. Anterior chamber cell count
- 7. Anterior chamber cell flare
- 8. Insert Visualization

Day 30 postop (+/- 7 days)

- 1. Concomitant medications
- 2. Best-corrected visual acuity as measured by ETDRS chart at 4m
- 3. Ophthalmic examination
- 4. Goldmann Intraocular pressure and CATS intraocular pressure
- 5. Subject reported AEs after surgery
- 6. Anterior chamber cell count
- 7. Anterior chamber cell flare
- 8. Insert Visualization
- 9. Ocular Comfort Index

3 month postop (+/- 14 days)

- 1. Concomitant medications
- 2. Best-corrected visual acuity as measured by ETDRS chart at 4m
- 3. Ophthalmic examination
- 4. Goldmann Intraocular pressure and CATS intraocular pressure
- 5. Corneal endothelial specular microscopy
- 6. Subject reported AEs after surgery
- 7. Anterior chamber cell count
- 8. Anterior chamber cell flare
- 9. Insert Visualization
- 10. OCT RNFL & Macula
- 11. Visual field mean deviation
- 12. Gonioscopy
- 13. Ocular Response Analyzer
- 14. Ocular Comfort Index
- 15. Indirect ophthalmoscope

5.2.2 Unscheduled Visits

All attempts should be made to keep patients on the study schedule. Unscheduled visits may be necessary to repeat testing following abnormal laboratory results, for follow-up of AEs, or for any other reason, as warranted.

5.2.3 Adverse Event Information Collection

The investigator (or designee) will record all AEs that occur during the study The definition of an AE and SAE, and information on the determination of severity and relationship to treatment are provided in Section 7.

5.3 Rescue Criteria

Rescue criteria include any of the following: moderate to severe photophobia, moderate to severe ciliary or conjunctival injection, or excessive anterior chamber cells or flare.

Rescue treatment would include supplementary prednisolone acetate 1% drops and/or topical NSAIDs, at the discretion of the study doctor.

6. RISK/BENENFIT ASSESSMENT

6.1 Risks

Use of corticosteroids on the eye, whether they are steroid drops or sustained-release inserts like DEXTENZA®, can worsen glaucoma with damage to the optic nerve by increasing intraocular pressure. Corticosteroids may suppress the host immune system and increase risk for bacterial infection, fungal infection, and viral infection. The use of steroids after eye surgery may delay healing and increase the incidence of bleb formation. DEXTENZA® may be ineffective. DEXTENZA® may cause discomfort in the eye. DEXTENZA® may involve unforeseeable risks. DEXTENZA® may involve additional risks that are currently unknown. Because DEXTENZA® is FDA approved for the treatment of postoperative ocular inflammation and pain, minimal overall risk to patients is anticipated.

6.2 Prevention of Risks

At each follow-up visit, risks will be monitored through conversations with the participant regarding their postoperative issues and visualized thorough all components of the ophthalmic exam (please see Table 1). Rescue treatment will be administered as per the criteria of section 5.3.

6.3 Benefits

For the eye receiving DEXTENZA®, a potential benefit is that the participant will not have to take steroid eye drops in that eye after surgery. DEXTENZA® may potentially be more comfortable and/or convenient than steroid eye drops. The results of this study will benefit future patients by providing clinical evidence comparing the safety and efficacy of DEXTENZA® to steroid eye drops in eyes with glaucoma and a cataract.

6.4 Alternative Treatments

Steroid eye drops are the standard-of-care alternative to DEXTENZA®. Also, DEXYCU® is another type of sustained-release dexamethasone drug that is currently FDA-approved for the same indication as DEXTENZA®. DEXYCU® is injected inside the eye, behind the iris of the eye. No currently published study has compared DEXTENZA® to DEXYCU®, so the relative advantages and disadvantages are not clearly known.

7. SAFETY DEFINITIONS, REPORTING, AND MONITORING

7.1 Definitions

7.1.1 Adverse Event

An AE is any untoward medical occurrence in a patient administered a study drug which may or may not have a causal relationship with the study drug. Therefore, an AE is any unfavorable and unintended sign (including abnormal laboratory finding), symptom, or disease which is temporally associated with the use of a study drug, whether or not considered related to the study drug.

An AE also includes any worsening (i.e. any clinically significant change in frequency and/or intensity) of a pre-existing condition that is temporally associated with the use of the study drug.

7.1.2 Serious Adverse Event

A SAE is any untoward medical occurrence that at any dose:

- Results in **death** includes all deaths, even those that appear to be completely unrelated to study drug (e.g. a car accident in which a patient is a passenger).
- Is **life-threatening** in the view of the investigator, the patient is at immediate risk of death at the time of the event. This does not include an AE that had it occurred in a more severe form, might have caused death.
- Requires in-patient **hospitalization** or prolongation of existing hospitalization. In-patient hospitalization is defined as admission to a hospital or an emergency room for longer than 24 hours. Prolongation of existing hospitalization is defined as a hospital stay that is longer than was originally anticipated for the event, or is prolonged due to the development of a new AE as determined by the investigator or treating physician.
- Results in persistent or significant **disability/incapacity** (substantial disruption of one's ability to conduct normal life functions).
- Is a congenital anomaly/birth defect
- Is an **important medical event** Important medical events may not be immediately life-threatening or result in death or hospitalization, but may

jeopardize the patient or may require intervention to prevent 1 of the other serious outcomes listed above (e.g., intensive treatment in an emergency room or at home for allergic bronchospasm; blood dyscrasias or convulsions that do not result in hospitalization; or development of drug dependency or drug abuse). Any malignancy (other than basal cell skin cancers) would be considered a medically important event.

7.2 Recording and Reporting Adverse Events

All AEs and SAEs will be recorded only if they are medically relevant.

All SAEs, regardless of assessment of causal relationship to study insert will be reported to Ocular Therapeutix.

To report an SAE, Ocular Therapeutix will be contacted at the following:

[contact]

SAE [contact]

The investigator will promptly report to the IRB all unanticipated problems involving risks to patients. This includes death from any cause and all SAEs related to the use of the study insert. All SAEs will be reported to the IRB, regardless of assessed causality.

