In terms of primary study endpoints, change in IOP values at 1 and 3 months are crucial for quantifying glaucoma outcome differences between groups. We will use three methods to comprehensively assess IOP changes, including Goldmann applanation tonometry, CATS tonometer prism, and the automatic IOP readings provided by the ocular response analyzer. Goldmann is the current standard of care, and thus will be the primary measure. However, CATS tonometry is a valuable supplement because it utilizes a modified prism that may better account for central corneal thickness and corneal hysteresis when providing IOP measurements (McCaffertey et al. 2019). Change in number of glaucoma medications from preop to 3 months postop will be serve as an additional metric to compare glaucoma outcomes. BCVA measurements using an ETDRS chart at 4 meters will indicate whether DEXTENZA® placement in this population affects the visual acuity improvement conferred by an IOL and MIGS. Recording adverse events is necessary not only for the integrity of the study, but also for evaluating the safety of the DEXTENZA® insert for this study population.

supplementary prednisolone acetate 1% eye drops will be recorded to compare ocular inflammation between groups. Checking for absence of anterior chamber cells at 30 days will provide another measure of control of inflammation. Incidence of cystoid macular edema at three months will be used to compare macular health between groups.

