3. STUDY DESIGN

3.1 Study Description and Duration

This prospective, open-label, single-center, randomized, fellow-eye, October 18, 2020 Page 7

investigator-initiated clinical study seeks to investigate the safety and efficacy of the dexamethasone insert in glaucoma patients after concomitant MIGS and cataract surgery. After screening a given patient for inclusion and exclusion criteria, and gaining informed consent, the patient's eligible eye will be randomized to either receive the dexamethasone insert after concomitant cataract-MIGS or to receive prednisolone acetate 1% eye drops after concomitant cataract-MIGS. For participants who enroll only a single eye, block randomization will be performed to ensure that the type of MIGS surgeries will be balanced between the two treatment groups. This stratification is necessary because it is possible that different MIGS devices can confound endpoint measurements, such as IOP control. A stratified block randomization schedule will be developed in advance by the sub-investigator through a computer program, and each assignment will be placed in opaque, sealed envelopes that will be labeled with the stratifying MIGS category. The primary investigator will only open an envelope after a patient is enrolled and the MIGS type that is suitable for the patient is determined. In the few cases where a patient enrolls both eyes, the same MIGS surgery will be performed for each eye. Under such a circumstance, simple randomization will be sufficient to determine whether the first or second eye operated on will receive the dexamethasone insert. The other eye will be placed in the prednisolone acetate 1% eye drops group.

Per enrolled eye, the study period will last for approximately 90 days after surgery, consisting of four postop follow-up visits. At Day 1, Day 7, Day 30, and Day 90, primary and secondary endpoints will be assessed alongside standard-of-care procedures. Adjusting for enrollment period, the study will last a total of approximately twelve months.

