8.2 Primary and Secondary Endpoints

Primary Endpoints

Effect of dexamethasone insert through Day 90 as measured by -

- 1. Mean Reduction in IOP at 1 and 3 months as measured by Goldmann Applanation Tonometer and comparison between groups
- 2. Mean change in ETDRS BCVA at 1 and 3 months and comparison between groups
- 3. Difference in adverse events between the two groups
- 4. Difference in number of glaucoma medications between the wo groups at 3 months

Secondary Endpoints

Through Day 90 as measured by -

- 1. Number of patients requiring supplemental prednisolone acetate 1% eye drops
- 2. Incidence of CME at 90 days as seen on OCT

- 3. Difference in Ocular Comfort Index between the two groups at 1 month and 3 months
- 4. Difference in percentage of patients with absence of anterior chamber cells at 30 days between groups

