9. STATISTICAL PLAN

Primary endpoints and secondary endpoints will be analyzed through statistical hypothesis testing. Demographic and baseline characteristics will be summarized descriptively. Continuous variables will be summarized with mean, median, and standard deviation. Categorical variables will be summarized with frequency and percentage.

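### Section 7.2 records adverse events only if judged medically relevant, with no criterion, although Section 5.2.3 records all of them and they feed a tested primary endpoint in an open-label trial

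*Combined protocol and SAP*

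**What the plan says.** The protocol has two operative rules for recording adverse events.

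- Section 5.2.3: "The investigator (or designee) will record all AEs that occur during the study".
- Section 7.2: "All AEs and SAEs will be recorded only if they are medically relevant".

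Section 7.1.1 defines an AE broadly, as "any unfavorable and unintended sign (including abnormal laboratory finding), symptom, or disease which is temporally associated with the use of a study drug". No causal link is required. Section 7.2 also requires all serious adverse events (SAEs) to go to the insert supplier, and adds "All SAEs will be reported to the IRB, regardless of assessed causality".

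These records feed the analysis. The third primary endpoint in Section 8.2 is "Difference in adverse events between the two groups", and Section 9 says "Primary endpoints and secondary endpoints will be analyzed through statistical hypothesis testing". Section 1.5 gives AE recording a central role: "Recording adverse events is necessary not only for the integrity of the study", and also for judging the insert's safety in this population. Section 3.1 describes the design as "This prospective, open-label, single-center, randomized, fellow-eye".

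**The concern.** Site staff cannot follow both recording rules. If they follow Section 7.2, someone must decide whether each event is relevant enough to enter the record, without a written threshold.

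That person is likely to know the arm. The trial is open label, the investigator or a designee records AEs, and insert visualization is scheduled at the same Day 1, 7, 30 and 90 visits as AE collection. No masked review of AEs is described.

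A filter of this kind, applied with the arm known, can create a difference in a primary endpoint or hide a real one. An event that never enters the AE record is hard to restore at analysis. The study was motivated by surgeons' concerns about the insert's safety (Section 1.3), so the AE comparison matters to its readers.

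**Working it through.** **1. The two rules side by side.** Section 5.2.3 has no filter; Section 7.2 has an only-if filter. Both are current text.

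**2. Is there a criterion elsewhere?** No. The phrase occurs only in Section 7.2. The one threshold in Section 7.1.1, clinical significance, applies to worsening of a pre-existing condition and not to AEs in general. Section 5.2.3 refers the reader to Section 7 for severity and relationship rules, but Sections 7.1 to 7.2 contain none.

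**3. Could Section 7.2 merely restate the definition?** No. An only-if condition on events that already count as AEs either removes some of them or does nothing.

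**4. Is Section 7.2 consistent with itself?** Not for SAEs. It filters them at recording and then requires all of them to be reported. Section 7.1.2 also counts every death, even an unrelated one.

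**5. Illustration of size.** The plan has no figure to reproduce: it states no AE rate, unit, test or alpha for this endpoint.

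- From the documents: 20 eyes per arm (Section 1.5).
- Assumed: the measure is the proportion of eyes with an AE; at most one event per eye; independent eyes (although some patients may contribute both); two-sided Fisher exact test at 0.05; full recording in one arm and a fraction *f* recorded in the other.

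Recorded rate in the filtered arm = true rate × *f*. Spurious gap = true rate × (1 − *f*). The probability of rejection is summed exactly over all pairs of binomial outcomes.

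False-positive rate when the true rate is the same in both arms:

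| True rate | f = 100% | 90% | 75% | 60% |
|---|---|---|---|---|
| 10% | 1.2% | 1.1% | 1.2% | 1.4% |
| 20% | 2.3% | 2.4% | 3.3% | 5.2% |
| 40% | 2.4% | 2.9% | 5.9% | 12.3% |
| 60% | 2.4% | 3.2% | 8.5% | 21.0% |

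At a 40% true rate the recorded comparison is 36% against 40% at *f* = 90%, 30% against 40% at 75%, and 24% against 40% at 60%. At *f* = 75%, true rates of 20%, 40% and 60% give spurious gaps of 5, 10 and 15 points.

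*Hiding a real difference.* Take true rates of 20% against 60%, with 75% recorded in the higher arm only. The recorded rate there is 0.60 × 0.75 = 45%, and power falls from 65.0% to 29.3%.

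*Several events per eye.* Suppose each affected eye has two events, each recorded independently. At *f* = 60% the recorded rate is 0.40 × (1 − 0.40²) = 33.6% against 40%, and the false-positive rate is 3.8%. At *f* = 75% it is 0.40 × (1 − 0.25²) = 37.5% against 40%, and 2.6%.

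*A filter applied equally in both arms.* The effect can go either way. Random loss of 25% in both arms turns 20% against 60% into 15% against 45%, and power falls from 65.0% to 44.3%. Now assume relevant AEs in 10% against 40% of eyes, plus independent trivial AEs in 30% of eyes in both arms. Recording everything gives 1 − 0.9 × 0.7 = 37% against 1 − 0.6 × 0.7 = 58%, with power 16.0%. Recording only relevant events gives 10% against 40%, with power 49.2%.

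**The case against.** Several points on the other side have force.

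- Section 7.1.1 defines an AE but does not say what is recorded. Section 7.2 therefore narrows that definition without negating it. This stands; the direct contradiction is with Section 5.2.3, and that is enough.
- Some unrecorded events could be recovered. Section 10.4 says patient data are extracted from the electronic medical record, and Table 1 schedules the ophthalmic examination, flare and concomitant medications at every follow-up visit whatever is judged relevant. Intraocular pressure, visual acuity, cystoid macular edema on OCT and anterior chamber cells also bypass the filter. This stands in part: the exposure is mainly to non-serious, symptom-type events. Retrieval from charts is not guaranteed, and the plan does not provide for it.
- The calculations rest on assumed inputs. At a 10% true rate, or with several events per affected eye, the effect is small, and the larger figures need heavy loss in one arm only. This stands; the figures show what is possible and do not carry the conclusion.
- Primary endpoint 3 has no stated unit or test, and deleting the phrase does not supply one. True, but that is a separate issue.
- Relevance kept as an attribute would still be judged open label. True, but the judgement would then be visible and would no longer decide which events exist in the data.

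**Conclusion.** The concern holds, and the text must be corrected. Sections 5.2.3 and 7.2 give incompatible recording rules. The restrictive one has no criterion, conflicts with its own section's SAE reporting, and governs what enters one of four primary endpoints in an open-label trial. This conclusion rests on the text alone.

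Differential recording is a risk and has not been shown to occur. Its direction and size cannot be derived from the documents. Under the assumptions above, with one arm fully recorded and the other at 75%, the false-positive rate ranges from 1.2% to 8.5% for true rates of 10% to 60%, against 1.2% to 2.4% with full recording in both arms.

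**What to change.** In Section 7.2, delete the relevance condition and state that every AE and SAE meeting the Section 7.1.1 definition is recorded in both arms, in line with Section 5.2.3. Add one sentence making medical relevance a recorded attribute of each event and not a condition for recording it. All AEs and relevant AEs can then both be tabulated by arm.

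The cost is one deletion, one added sentence and some more AE lines. Table 1 already collects AEs at every follow-up visit, so no visit is added. The change does not remove open-label bias in what patients report or staff elicit.
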